9.0 Adverse Events and Reporting Requirements

Adverse event definition:

An adverse event is the appearance or worsening of any undesirable sign, symptom, or medical condition occurring after starting the study drug even if the event is not considered to be related to study drug. Medical conditions/diseases present before starting study drug are only considered adverse events if they worsen after starting study drug. Abnormal laboratory values or test results constitute adverse events only if they induce clinical signs or symptoms, are considered clinically significant, or require therapy and otherwise meet the criteria for a reportable adverse event as defined above. They are to be captured under the signs, symptoms or diagnoses associated with them.

It is common for HCT recipients to experience multiple complications as part of the transplant itself that are unrelated to exposure to investigational agents. Symptoms of the original or targeted disease are not to be considered adverse events for this study except for hematological toxicities as defined below. From start of study treatment through 30 days from last dose of CYT107, symptoms related to the conditioning regimen will not be reported unless the event is both serious and considered by the investigator to also be possibly, probably, or definitely related to CYT107. After 30 days from the last dose of CYT107, adverse events should only be reported if they are both serious and probably or definitely related to CYT107. Events that are unlikely or unrelated to CYT107 are not required to be reported. Reporting of such events should include the investigator's assessment as to whether the event should be attributed to any of the HCT procedure itself, CYT107, GVHD, or exposure to immunosuppressive agents. An event may be attributable to all, some, or one of these categories.

Assessment of the Adverse Events Severity:

The severity of the adverse events (AEs) will be graded according to the Common Terminology Criteria v4.0 (CTCAE).

Recommended Adverse Event Recording Guidelines

Attribution	Grade 1	Grade 2	Grade 3	Grade 4	Grade 5
Unrelated	Phase I	Phase I	Phase I Phase II	Phase I Phase II Phase III	Phase I Phase II Phase III
Unlikely	Phase I	Phase I	Phase I Phase II	Phase I Phase II Phase III	Phase I Phase II Phase III
Possible	Phase I Phase II	Phase I Phase II Phase III			
Probable	Phase I Phase II Phase III				
Definitive	Phase I Phase II Phase III				

Treatment period:

Active treatment period (ATP) is defined from the first injection of CYT107 through 30 days from

the last injection.

Time for Adverse Event (AE) Collection:

Adverse events will be collected from the first injection of CYT107 through 30 days from the last injection. AEs that occur up to 30 days from the last injection of CYT107 will be followed until resolution.

The collection of adverse events will reflect the onset and resolution date and maximum grade. If a patient is taken off study while an event is still ongoing, this will be followed until resolution or the event has stabilized. Pre-existing medical conditions will be recorded only if an exacerbation occurs during the active treatment period. Co-morbid events will not be scored separately.

Adverse Event Reporting:

The Investigator or physician designee is responsible for verifying and providing source documentation for all adverse events, and assigning attribution for each event on all subjects enrolled on this study.

Adverse events will be documented and entered into the electronic case report form (REDCap/CORe). All protocol specific data will be entered into REDCap/CORe.

Events not to be considered adverse events in this study are those related to original disease or expected in the post-allogeneic transplant period.

Isolated changes in laboratory parameters such as electrolyte, magnesium and metabolic imbalances, uric acid changes, elevations of GPT, GOT, LDH and alkaline phosphatase will not be captured.

Concomitant medications

Patients treated on this protocol will require supportive care treatment (concomitant medications). These medications are considered standard of care and have no scientific contribution to the protocol; therefore no data will be captured on various medications needed or their side effects. All concomitant medications will be captured in the medical record.

Causality Assessment.

The principal investigator will be the final arbiter in determining the causality assessment.

List of most common expected adverse events:

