4.0 Treatment Plan and Study Design

CYT107 will not be administered before Day 60 but could be started as late as Day 180 post-CBT or haplo-SCT.

The active treatment period will be from the first injection of CYT107 and for 30 days after the last injection. The follow-up period will be for three years after the last injection.

Patients will be treated with CYT107 by intramuscular route (I.M.)* post CBT or haplo-SCT (from 60 to 180 days), with 1 of 3 doses below:

- 5 mcg/kg/dose for 3 doses, one week apart
- 10 mcg/kg/dose for 3 doses, one week apart
- 20 mcg/kg/dose for 3 doses, one week apart

Enrollment of the first 3 participants will be staggered by 14 days. Accrual in between cohorts will be halted for 30 days after the last patient in each cohort has received the last dose of CYT107.

* If the patient's platelet count is below 35,000, the product may be administered by subcutaneous route.

All patients will receive foscarnet for the management of CMV infection as per Stem Cell Transplantation and Cellular Therapy Department's standard of care.

Dose modifications

Treatment will be permanently discontinued for patients developing grade 3 or 4 GVHD, secondary graft failure, disease relapse, PTLD, PML, grade 2-4 skin rash, or grade 3-4 non-hematological toxicity attributable to CYT107.

Patients who develop grade 2 non-hematological toxicity attributable to the CYT107 will have the next dose withheld until the toxicity resolves to grade 1. If the toxicity resolves within 2 weeks the drug will be administered at the same dose, however if the toxicity takes more than 2 weeks to resolve the drug will be administered at the next lower level, or permanently discontinued if the patient was already at the lowest level. If the toxicity takes more than 4 weeks to improve to grade 1, the CYT107 will be permanently discontinued

For patients who at study entry have grade 0, 1 or 2 hematological toxicity and develop grade IV hematological toxicity attributable to the CYT107 will have the next dose withheld until the toxicity resolves to grade 2. If the toxicity resolves within 2 weeks the drug will be administered at the same dose, however if the toxicity takes more than 2 weeks to resolve the drug will be administered at the next lower level, or permanently discontinued if the patient was already at the lowest level. If the toxicity takes more than 4 weeks to improve to grade 2, the CYT107 will be permanently discontinued

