6. PT/PTT
7. Electrolytes
8. Physical exam
9. Medical history

6.2 Evaluation after CYT107 administered:

Weekly until day +42 following CYT107:

1. CBC, differential, platelets
2. SGPT, calcium, glucose, uric acid, magnesium, serum bilirubin, BUN and creatinine, serum protein, albumin, ALT, alkaline phosphatase, electrolytes, tacrolimus levels.
3. Physical examination
4. Adverse event assessment

6.3 Viral Infections. Patients will be monitored for viral infections after the CYT107.

1. CMV by PCR will be assayed in the blood weekly from the start of IL-7 therapy until day 180 from the start of IL-7 therapy.
2. EBV PCR will be assayed in the blood every two weeks from day 60 until day 100 and then monthly until day 180 from the start of IL-7 therapy.
3. BKV PCR will be assayed in the urine and blood if patients become symptomatic, as clinically indicated.

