7.0 Statistical Considerations

7.1 Outcomes and Covariates

7.1.1 Primary Outcomes

Toxicity. Dose limiting toxicity (DLT) is defined as any of the following events: grade 3 or 4 GVHD, secondary graft failure, disease relapse, development of PTLD, development of PML, grade 2 organ failure or grade 2-4 skin rash, fatigue, AST and ALT elevations, allergic anaphylaxis, or hemolytic anemia, attributable to CYT107, or death, occurring within 42 days of the first CYT107 injection.

Biological Responses. The absolute number and percentage of total White Blood Cells (WBCs) consisting of T-cells and of B-cells will be observed at 1, 3, 6, 9 and 12 months.

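### The DLT window and the adverse-event collection window agree only for patients dosed on schedule, so early stopping or held doses can leave a DLT unrecorded or uncounted

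*Combined protocol and SAP*

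**What the plan says.** - **DLT window.** Section 7.1.1 counts a listed event as a DLT when it is "occurring within 42 days of the first CYT107 injection". The list includes grade 2-4 skin rash and fatigue, which need not be serious. Section 7.3.2 uses each patient's day-42 status to open the second cohort and the seventh place at a dose. Section 7.7 times the toxicity summary at 42 days after the first injection.
- **Collection window.** Section 9.0 states: "Adverse events will be collected from the first injection of CYT107 through 30 days from the last injection". Serious events have the same end point. After it, Section 9.0 restricts reporting to events that are serious and also probably or definitely related. It separately asks that late related serious events still reach the IND Office.
- **Scheduled assessment.** Section 6.2 lists an adverse event assessment under "Weekly until day +42 following CYT107". It does not say whether day +42 is counted from the first or the last injection.
- **Dosing and holds.** Section 4.0 spaces injections identically at every level, for example "10 mcg/kg/dose for 3 doses, one week apart". For a grade 2 non-hematological toxicity, the next dose is held: "If the toxicity takes more than 4 weeks to improve to grade 1, the CYT107 will be permanently discontinued". For a grade IV hematological toxicity: "If the toxicity takes more than 4 weeks to improve to grade 2, the CYT107 will be permanently discontinued". Recovery within 2 weeks means the same dose. Slower recovery means the next lower level, or permanent discontinuation at the lowest level.
- **Accrual halt.** Section 4.0 also stops accrual between cohorts until 30 days after a cohort's last patient has had the last dose.

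**The concern.** One window is anchored to the first injection and the other to the last. Nothing in the plan links them when dosing stops early or is delayed. DLT is the primary safety outcome, and its count drives the within-dose stopping rule. With at most seven patients initially planned per dose, one DLT can decide whether a dose stays open. A patient whose events were not collected to day 42, or whose third injection came on or after day 42, can enter that count as free of toxicity without having been observed for as long as a patient dosed on schedule.

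**Working it through.** The plan states no figure for the overlap of the windows, so the check is day arithmetic. Day 0 is the first injection.

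**Inputs.** Planned injections on days 0, 7 and 14 (4.0). DLT window ends on day 42 (7.1.1). Collection ends on day of last injection + 30 (9.0). A held dose can be given up to 28 days late above the lowest level and up to 14 days late at the lowest level (4.0), counting the hold from the due date.

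**Step 1: collection against the DLT window.** Uncovered days = 42 − (last injection + 30), if positive.

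| Injections given | Collection ends | Uncovered part of the 42 days |
|---|---|---|
| Three, on schedule | 14 + 30 = 44 | none |
| Two | 7 + 30 = 37 | 42 − 37 = 5 |
| One | 0 + 30 = 30 | 42 − 30 = 12 |

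In the uncovered days, a DLT that is not serious, or is only possibly related, fails the reporting filter in 9.0.

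**Step 2: day of dose 3 after holds.** DLT observation after dose 3 = 42 − day of dose 3, or zero if negative.

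| Dosing history | Dose 3 given | DLT observation | Collection ends |
|---|---|---|---|
| On schedule | 14 | 28 days | 44 |
| One 2-week hold, any level | 14 + 14 = 28 | 14 days | 58 |
| Two 2-week holds, any level | 7 + 14 + 7 + 14 = 42 | 0 | 72 |
| One 4-week hold, above the lowest level | 7 + 28 + 7 = 42, or 14 + 28 = 42 | 0 | 72 |
| Middle level: one 4-week and one 2-week hold | 7 + 28 + 7 + 14 = 56 | 0 | 86 |
| Top level: two 4-week holds | 7 + 28 + 7 + 28 = 70 | 0 | 100 |

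The middle level stops at day 56 because a hold longer than 2 weeks moves the patient to the lowest level, where only a 2-week hold is allowed. If the 4 weeks run from toxicity onset instead, one hold puts dose 3 between about day 35 (28 + 7) and day 42, and two from the top level put it at day 56 (28 + 28) or later.

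**Step 3: what one unrecorded DLT does to the stopping rule.** Under the beta(.35, .65) prior in 7.3.2, the posterior after y DLTs in n patients is beta(.35 + y, .65 + n − y). Accrual stops if Pr[p > .35] exceeds .85.

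- 3 of 3 gives .985 (stop); 2 of 3 gives .834 (continue).
- 4 of 5 gives .973 (stop); 3 of 5 gives .849 (continue).

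**Step 4: illustration only.** Applying the criterion at n = 3 to 6 (boundaries 3/3, 3/4, 4/5, 4/6) gives stopping probabilities of .165, .502 and .600 at true DLT rates of .35, .55 and .60. The table in 7.3.2 has .163, .497 and .601. At .65 the result is .694 against .607, a separate matter. If a share m of DLTs were missed, the effective rate is p(1 − m). At p = .60 the stopping probability falls from .600 to .483 (m = 10%), .369 (20%) or .266 (30%). These shares are assumptions, and spreading them over all patients is a simplification.

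**The case against.** - **Assessment to day 42 is already planned.** Section 6.2 schedules weekly adverse event assessment to day +42, Section 7.6 makes the team record all outcomes, and 7.7 requires a summary at day 42. This stands in large part: one cannot infer that DLTs after day 30 or 37 would simply not be looked for. But 6.2 leaves its anchor unstated, 9.0 sets a different end point with a restrictive filter, and 6.0 accepts missed time points for patients followed at home clinics.
- **Many holds and stops are already DLTs.** Grade 3-4 GVHD, relapse, graft failure and grade 2-4 rash both end treatment and appear in the DLT list. This stands, and it narrows the point to patients who stop for another reason (non-compliance or investigator judgment in 8.0) or are held for grade IV hematological toxicity other than hemolytic anemia, or for an unlisted grade 2 toxicity. It also means that a reader should not infer that the missed events are shown to be informative. The documents do not establish this.
- **The accrual halt.** A reader might infer that a patient with a delayed third dose releases the next cohort at day 42. The documents do not support that as a flat statement. If the cohort's last patient has dose 3 on day 42, the halt in 4.0 runs to 42 + 30 = day 72. The halt does not make a late event a DLT, however, and it sits beside a day-42 release rule in 7.3.2 with no statement of which governs.
- **Late dosing is not general.** Correct: day 70 needs a start at the top level and two maximal holds, and at the lowest level one hold takes dose 3 only to day 28.
- **A fixed 42-day window is a consistent choice.** Sections 7.1.1, 7.3.2 and 7.7 all use it. That explains the window but does not answer how a patient with dose 3 on or after day 42 should be scored.

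**Conclusion.** The concern holds for two limited groups; for patients dosed on schedule there is no gap (day 44 against day 42).

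1. **Unrecorded.** In a patient who stops after one or two injections for a non-DLT reason, a non-serious DLT such as grade 2 rash or fatigue in the last 12 or 5 days of the window may go unrecorded, because 6.2 and 9.0 do not agree.
2. **Uncounted.** In a patient held for a toxicity that is not a DLT, dose 3 can fall on day 42 or later. Its toxicity is then collected as an adverse event but lies outside the DLT definition, and the patient can count as free of toxicity under 7.3.2. No text in the plan corrects this.

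The day counts assume that holds run from the due date. The documents give no frequency of affected patients, so the effect on the stopping probabilities cannot be sized beyond the illustration. One unrecorded or uncounted DLT at the 3/3 or 4/5 boundary does change the decision, which makes alignment worthwhile at its small cost.

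**What to change.** - **Section 9.0:** collect adverse events to the later of day 42 after the first injection and 30 days after the last, and apply the restricted reporting filter only after that point. On-schedule patients stay at day 44; those stopped after one or two injections move from day 30 or 37 to day 42.
- **Section 7.1.1:** run DLT ascertainment to the later of day 42 after the first injection and 28 days after the last. On-schedule patients stay at 14 + 28 = day 42. With dose 3 on day 42, 56 or 70, ascertainment ends on day 70, 84 or 98, always inside the collection window.
- **Sections 6.2, 7.3.2 and 7.7:** conform the day-42 wording, and state the anchor in 6.2.
- **Section 4.0:** reconcile the 30-day accrual halt with the release rule in 7.3.2, and say which governs.

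Dose and hold rules are unchanged. The cost is wording in these sections and a longer wait for DLT evaluation in patients with holds, which may delay accrual at that dose. The change cannot recover data from a patient who withdraws consent to follow-up.

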3.0 Patient Eligibility

3.1 Patient Inclusion Criteria

1. Patient 18 years old or older.
2. English and non-English speaking patients are eligible.
3. Patient post a cord blood transplant (CBT) or haplo-SCT, mismatched unrelated donors (mMUDmatched), unrelated donors (MUDs), matched related donors (MRDs), both PB and marrow sources with documented absolute neutrophil engraftment.
4. Patients with documented engraftment but require G-CSF to treat myelosuppression induced by drugs used to treat or prevent infection are eligible.
5. Karnofsky performance status (KPS) > 60%.
6. Adequate organ function:
 - Pulmonary: Absence of dyspnea or hypoxia (< 90% of saturation by pulse oximetry on room air).
 - Hepatic: Bilirubin <= 1.5 X ULN, AST (SGOT) and /or ALT (SGPT) <= 2.5 X ULN. PT/PTT < 1.5 X ULN.
 - Renal: Calculated Creatinine clearance > 50 mL/min/1.73 m².
7. Diagnosis of acute myeloid leukemia; myelodysplastic syndrome; chronic myeloid leukemia; myelofibrosis or myeloproliferative disease.
8. Patients are allowed to enroll on this study if they are enrolled on another IND trial.

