2. EKG
3. Oxygen saturation by pulse oximetry
4. Creatinine
5. AST, ALT, bilirubin

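### AST and ALT elevations count as DLTs, but Section 9.0 excludes isolated rises from capture and the weekly post-dose panel omits AST

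*Combined protocol and SAP*

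**What the plan says.** **DLT definition.** Section 7.1.1 (Primary Outcomes) includes "AST and ALT elevations, allergic anaphylaxis, or hemolytic anemia, attributable to CYT107, or death, occurring within 42 days of the first CYT107 injection". The sentence does not make clear whether the grade range given for skin rash also governs the enzyme elevations.

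**Naming.** Section 3.1 pairs the names itself: "AST (SGOT) and /or ALT (SGPT". So SGOT/GOT is AST and SGPT/GPT is ALT.

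**Measurement.** The pre-treatment list in Section 6.1 has "AST, ALT, bilirubin". After dosing, Section 6.2 sets tests "Weekly until day +42 following CYT107", and the chemistry line reads "SGPT, calcium, glucose, uric acid, magnesium, serum bilirubin, BUN and creatinine, serum protein, albumin, ALT, alkaline phosphatase", followed by electrolytes and tacrolimus levels. AST (SGOT) is not there.

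**Capture.** Section 9.0, under Adverse Event Reporting, says that for isolated laboratory changes "elevations of GPT, GOT, LDH and alkaline phosphatase will not be captured". The adverse event definition in the same section says "Abnormal laboratory values or test results constitute adverse events only if they induce clinical signs or symptoms, are considered clinically significant, or require therapy", and adds: "They are to be captured under the signs, symptoms or diagnoses associated with them".

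**Use of the count.** Section 7.3.2 stops accrual to a dose when Pr[p(d) > .35 | data] exceeds .85 under a beta(.35, .65) prior, starting at n = 3. Section 7.3.1 plans 7 patients per dose.

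**The concern.** The DLT count is the primary safety outcome and the only input to the within-dose stopping rule. One part of the plan names transaminase elevation as a DLT, another tells staff not to capture it when it is isolated, and a third does not schedule one of the two enzymes after dosing. A DLT that consists only of a laboratory value is by nature an isolated change, so the exclusion covers exactly the case in which the elevation is the patient's only DLT.

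Two failures are possible. An AST-only DLT may never be measured. An ALT-only DLT would be measured weekly but may not be recorded as a DLT. Either would bias the reported DLT rate downward and weaken the stopping rule.

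**Working it through.** **1. The plan's own figures.** With x DLTs in n patients, the posterior is Beta(.35 + x, .65 + n − x). The smallest x giving Pr(p > .35) > .85 is 3, 3, 4, 4 at n = 3, 4, 5, 6. A dose can first reach a boundary at n ≤ 6 in three ways:

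- 3/3: probability p³
- 3/4 (two of the first three, then one more): 3(1 − p)p³
- 4/6 (two of the first four, then two more): 6p²(1 − p)² × p²

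The printed 4/5 cannot be a first crossing: four DLTs in five patients require at least three in the first four, which has already stopped the dose.

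| True p | 3/3 + 3/4 + 4/6 | Total | Printed in Section 7.3.2 |
|---|---|---|---|
| .35 | .043 + .084 + .038 | .164 | .163 |
| .55 | .166 + .225 + .111 | .502 | .497 |
| .60 | .216 + .259 + .124 | .600 | .601 |

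This reading of the rule reproduces these three rows closely. The fourth row (p = .65: computed .694, printed .607) does not reproduce. That is a separate matter and is not used here.

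**2. Effect of one uncounted DLT.**

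| True count | Pr(p > .35) | Count with one lost | Pr(p > .35) |
|---|---|---|---|
| 3/3 | .985 | 2/3 | .834 |
| 3/4 | .932 | 2/4 | .694 |
| 4/6 | .929 | 3/6 | .746 |
| 4/5 (as printed) | .973 | 3/5 | .8485 |

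Every value in the last column is below .85, so the stop at that look does not occur. A later look may still stop the dose. For example, a counted 2/3 becomes 3/4 if the next patient has a recorded DLT.

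**3. How long the dose-modification route works.** Section 9.0 (AEs Data Collection) sends SAEs and adverse events that require a dose modification to REDCap. With doses on days 0, 7 and 14 there is nothing left to modify after day 14. That leaves 42 − 14 = 28 of the 42 window days (28/42 = 67%) and the draws on days 21, 28, 35 and 42, which are 4 of 6. In that period a non-serious elevation has no such route.

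**4. Adverse event window against DLT window.** Section 9.0 collects adverse events to 30 days after the last injection. After three on-schedule doses this is day 14 + 30 = 44, which covers day 42. After one dose it is day 30, and after two it is day 7 + 30 = 37. Both end before the DLT window does.

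**5. Scheduled AST results after dosing.** 0 of 6 weekly draws.

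**6. Illustration under an assumption.** The documents do not give the share s of DLTs that would be transaminase-only and missed. If each DLT is lost independently with probability s, the recorded rate is p(1 − s). For s = 0, .10, .20 and .30, Pr(stop) is .502, .397, .299 and .212 at p = .55, and .600, .483, .369 and .266 at p = .60.

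**The case against.** The best reply is that the sections can be read together. The exclusion concerns adverse event reporting of isolated changes. An elevation that the investigator attributes to CYT107 and counts toward a stopping rule is hard to call clinically insignificant, so the adverse event definition would admit it. DLT is a primary outcome in its own right. Section 7.6 makes the investigator's team responsible for recording outcome variables, Section 7.7 requires toxicity summaries at 42 days, Section 6.2 has weekly adverse event assessments, and Section 9.0 sends protocol-specific data to REDCap. The recommended recording table lists phase I for every grade and attribution. Section 8.0 allows removal from study for attributable grade 3–4 non-hematological toxicity whether or not a dose remains. The missing AST is probably a slip for SGOT.

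Much of this stands as mitigation. A measured ALT elevation would often be noticed, and 67% of the window is the time for which one route is closed, not a period without any capture. But none of these provisions says that a DLT overrides the exclusion. The definition files an admitted laboratory value under its associated sign, symptom or diagnosis, and an asymptomatic elevation has none. The recording table is only recommended, and Section 8.0 is a removal rule, not a recording rule. No provision supplies an AST value that was not drawn.

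Two points on the arithmetic are fair. Losing one event at a boundary undoes the stop almost by construction, so the posteriors show sensitivity and not frequency. The 4/6 row also sits awkwardly with Section 7.3.2(b), which lets patient 7 enroll once two of six patients are free of toxicity. The 3/3 and 3/4 rows carry the point without it.

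**Conclusion.** The concern holds. This is a conflict between stated rules, and following the text literally can lose a primary-outcome event. The measurement gap is limited to AST; for ALT the risk is in recording. One lost DLT at a boundary cancels the stop at that look, with posteriors falling from .985 to .834 and from .932 to .694 against a cutoff of .85. These figures rest on the Section 7.3.2 criterion applied from n = 3, the reading that matches three of the four printed rows. The 28-day figure assumes on-schedule dosing. How often a transaminase elevation would be a patient's only DLT cannot be derived from the documents, and no rate of missed DLTs is claimed. The plan should be corrected, but nothing here shows that DLTs have been missed.

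A lesser wording conflict lies nearby. Section 9.0 says events related to the original disease or expected after transplant are not adverse events, yet it lists GVHD and secondary graft failure as expected adverse events, and Section 7.1.1 makes grade 3–4 GVHD, secondary graft failure and relapse DLTs. These events are also tracked elsewhere (Sections 1.0, 4.0, 7.1.2 and 8.0), so an under-count is unlikely.

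**What to change.** - **Section 6.2:** replace the duplicate SGPT/ALT entry with AST and ALT, and say which injection day +42 is counted from.
- **Section 9.0:** state that any event meeting the Section 7.1.1 definition, including AST and ALT elevations, is recorded in REDCap as that DLT component through day 42 of the first injection, regardless of the laboratory and expected-event exclusions and of how many doses were given.
- **Section 7.1.1:** state whether the grade range applies to AST and ALT elevations, so that the recording rule can be applied.
- **Clarification:** reconcile the Section 9.0 sentence on disease-related and expected events with its own list of expected adverse events and with the DLT definition.

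The cost is wording plus 6 draws × 21 patients = 126 AST results from blood already drawn, if day +42 runs from the first injection. If it runs from a third dose on day 14, there are 8 draws and 8 × 21 = 168 results.
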